5. TREATMENT PLAN

5.1 Agent Administration

Treatment will be administered on an outpatient basis. Reported adverse events and potential risks are described in [Section 7](#). Appropriate dose modifications are described in [Section 6](#). No investigational or commercial agents or therapies other than those described below may be administered with the intent to treat the patient's malignancy, except for hydroxyurea. Prophylactic intrathecal chemotherapy is allowed if determined to be clinically necessary. Please see section 6.5 for details on IT chemotherapy prophylaxis.

This is a standard 3+3 dose escalation study with two patient cohorts, separated by transplant status (Arm A = post allo-HSCT; Arm B = transplant naive). Given the concern for potential toxicity in the post allo-HSCT arm (Arm A), we will first demonstrate safety at the first dose level (e.g. **Dose Level 0**; starting dose, see table in Section 5.1 below) with patients on Arm B (transplant naive cohort) prior to Arm A enrollment. If there is no DLT in the first 3 patients, then we will proceed to enrollment on Arm A at the first dose level. However, if there is a DLT event in the first 3 patients assessed in Arm B, then following 3+3 rules, an additional 3 patients (a total of 6) will be tested at the same dose level. If there are no additional DLTs within those 6 patients, then we will allow enrollment on Arm A.

After the first dose level is assessed for safety in Arm B, then subjects can be simultaneously enrolled to the appropriate arm with no further observation period or delay between the start of therapy for each enrolled patient in either arm. Overall, patients in Arm A and Arm B will be tested at the same three dose levels, as described in the table below ([section 5.1](#)).

In the event that 0 of 3 patients in a dose level experience a DLT, the dose level may still be expanded to 6 evaluable patients based on observed toxicity at the current dose level at the discretion of the overall PI to capture patient safety prior to expanding.

Dose Escalation Schedule for both Arm A and Arm B		
Dose Level	Dose	
	Ipilimumab (mg/kg) on day 1	Decitabine* (mg/m ²) on days 1-5
Level -1 (dose de-escalation)	1	20
Level 0 (starting dose)	3	20
Level 1	5	20
Level 2	10	20

*Decitabine is NOT dose-escalated and will be given at standard dosing of 20 mg/m² IV daily x 5 consecutive doses on days 1-5 of a 28-day cycle

Treatment Overview

- Each cycle is 28 days in length

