5.2 Definition of Dose-Limiting Toxicity

DLT for dose-escalation purposes will be determined during the first 8 weeks of combination therapy (56 days from start of combination, starting cycle 1 day 1 of ipilimumab and decitabine) during the induction phase only. A DLT will be defined as any of the following toxicities that are determined to be *at least possibly* related to treatment with combination ipilimumab and decitabine and not related to underlying disease or intercurrent illness or to decitabine alone. Adverse events that occur after the first 8 weeks will also be evaluated by the investigator and may be considered dose limiting depending on the clinical scenario. Events will be graded by CTCAE v5.0 criteria.

DLTs include:

- Any study treatment related death (not due to disease or intercurrent illness).
- Acute GVHD that is an overall grade III or higher (see [Appendix B](#))
 - Exception: For skin GVHD alone, must be an overall grade II with at least stage 3 involvement or higher to be considered a DLT (skin GVHD that is stage 1-2 will not be considered a DLT).
- Grade 3 or higher non-hematologic toxicity
 - Exceptions:
 - Fatigue, nausea, weight loss, electrolyte abnormalities managed by replacement or correction, endocrine abnormalities managed by replacement therapy, skin rash, and those attributable to GVHD (as above)
 - Infections will be considered a DLT if grade 4 or higher or grade 3 that does not recover to grade 1 within 4 weeks
- Admission and IV antibiotics for neutropenic fever without sepsis or severe complication will not be considered a DLT (this is a frequent complication of underlying disease and of decitabine therapy)
- Grade 3 immune-related adverse events (e.g. diarrhea, pruritus, rash, endocrinopathies) that respond to corticosteroids and improve to grade 1 or less within 4 weeks will NOT count as DLTs. Optional biopsy of affected organs will be encouraged to help determine whether the immune-related condition is due to direct effects of ipilimumab versus GVHD.
- Grade 3 ipilimumab infusion reactions; a second consecutive occurrence or grade 4 or high infusion reaction will be considered a DLT.
- Grade 4 or higher hematologic toxicity will be considered a DLT if patients do not recover their absolute neutrophil count to $\geq 500 \times 10^9/L$ or platelet count to $\geq 25,000 \times 10^9/L$, at the end of the DLT window, with a hypocellular marrow and absence of

underlying disease.

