- Autoimmune/inflammatory events are presumably related to the mechanisms of action of ipilimumab and potentially to a therapeutic effect. The incidence and severity of these events may be dose related, but once initiated, there is no evidence that lowered doses can be administered without continued autoimmune activity and there has so far been no demonstrable benefit to continuing ipilimumab after an autoimmune event during the initial treatment. The significance and benefit of toxicity or continued treatment in the maintenance phase has not been determined. Typically no dose modification is used for ipilimumab.

Permanent Discontinuation of Ipilimumab for Related Adverse Events

If discontinuing ipilimumab, participants will have the option to continue decitabine alone on study if they are determined to be clinically benefitting from treatment at the investigator's discretion.

Permanently discontinue ipilimumab for any of the following:

- Grade III or higher acute GVHD.
- Persistent adverse reactions that requires holding more than 2 ipilimumab doses (exception: patients with a GVH event(s) that is determined to be less than a grade III who are benefitting from study treatment can continue on study after approval from overall PI).
- Any persistent grade 3 or 4 event (see exceptions below in [section 6.2.1](#)).
- Any immune related AE that is grade 3 or higher requiring systemic corticosteroids at a dose of 1 to 2 mg/kg/day of prednisone or equivalent. Immune related AEs that were

grade 2 or less are allowed to stay on study and receive corticosteroids if necessary so as long as they are tapered off by next scheduled dose of ipilimumab. They cannot be delayed by more than 4 weeks (meaning 8 weeks between doses), or they have to come off study.

- Severe or life-threatening adverse reactions, including any of the following:
 - Colitis with abdominal pain, fever, ileus, or peritoneal signs; increase in stool frequency (7 or more over baseline), stool incontinence, need for IV hydration for more than 24 hours, gastrointestinal hemorrhage, and gastrointestinal perforation
 - Aspartate aminotransferase (AST) or alanine aminotransferase (ALT) >5 times the upper limit of normal or total bilirubin >3 times the upper limit of normal
 - Stevens-Johnson syndrome, toxic epidermal necrolysis, or rash complicated by full thickness dermal ulceration, or necrotic, bullous, or hemorrhagic manifestations

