6.3.1 Treatment of Infusion Reactions Associated with Ipilimumab

Since ipilimumab contains only human protein sequences, it is less likely that any allergic reaction will be seen in patients. However, it is possible that infusion of ipilimumab will induce a cytokine release syndrome that could be evidenced by fever, chills, rigors, rash, pruritus, hypotension, hypertension, bronchospasm, or other symptoms. No prophylactic pre-medication should be given unless indicated by previous experience in an individual patient. Reactions should be treated based upon the following recommendations.

- For mild symptoms (e.g., localized cutaneous reactions such as mild pruritus, flushing, rash):
 - Decrease the rate of infusion until recovery from symptoms, remain at bedside and monitor patient.
 - Complete the ipilimumab infusion at the initial planned rate.
 - Diphenhydramine 50 mg IV may be administered at the discretion of the treating physician and patients may receive additional doses with close monitoring.
 - Premedication with diphenhydramine may be given at the discretion of the investigator for subsequent doses of ipilimumab.
- For moderate symptoms (any symptom not listed above [mild symptoms] or below [severe symptoms] such as generalized pruritus, flushing, rash, dyspnea, hypotension with systolic BP >80 mmHg):
 - Interrupt ipilimumab.
 - Administer diphenhydramine 50 mg IV.

- Monitor patient closely until resolution of symptoms.
- Corticosteroids may abrogate any beneficial immunologic effect, but may be administered at the discretion of the treating physician.
- Resume ipilimumab infusion after recovery of symptoms.
- At the discretion of the treating physician, ipilimumab infusion may be resumed at *one half the initial infusion rate, then increased incrementally to the initial infusion rate.*
- If symptoms develop after resumption of the infusion, the infusion should be discontinued and no additional ipilimumab should be administered that day.
- The next dose of ipilimumab will be administered at its next scheduled time and may be given with pre-medication (diphenhydramine and acetaminophen) and careful monitoring, following the same treatment guidelines outlined above.
- At the discretion of the treating physician additional oral or IV antihistamine may be administered prior to dosing with ipilimumab.
- For severe symptoms (e.g., any reaction such as bronchospasm, generalized urticaria, systolic blood pressure <80 mm Hg, or angioedema):

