 - Immediately discontinue infusion of ipilimumab, and disconnect infusion tubing from the subject.
 - Consider bronchodilators, epinephrine 1 mg IV or subcutaneously, and/or diphenhydramine 50 mg IV, with solumedrol 100 mg IV, as needed.
 - Patients should be monitored until the investigator is comfortable that the symptoms will not recur.
 - No further ipilimumab will be administered.
- In case of late-occurring hypersensitivity symptoms (e.g., appearance within one week after treatment of a localized or generalized pruritus), symptomatic treatment may be given (e.g., oral antihistamine, or corticosteroids).

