The MTD will be the highest dose at which 1 or fewer of 6 patients experience a DLT. If no MTD has been established, then dose level 2 will be used in the dose expansion cohort as the recommended phase 2 dose (RP2D). Once an MTD (or RP2D) has been established an expansion cohort will be enrolled for each arm. For a given arm, if all 3 dose cohorts are filled to 6 patients, then a 6 patient expansion will be added. If 2 or fewer dose cohorts are filled to 6 patients, then a 12 patient expansion will be added so that no more than 24 patients (dose escalation + expansion) will be treated on a given arm. Patients will be monitored for DLTs during the first 8 weeks of combination therapy (56 days from start of combination) during the induction phase only. If a patient experiences disease progression in cycle 1, the patient will be evaluable for DLT if the patient completes a minimum of 28 days. Any patient who does not complete cycle 1 for any reason other than DLT will be considered non-evaluable for dose escalation decisions and will be replaced by an additional patient at that same dose level. Patients in cycle 2 will be assessed for DLT.

Safety and tolerability of decitabine plus ipilimumab will be evaluated by means of drug related DLT (defined as first 8 weeks of combination treatment with decitabine and ipilimumab), AE reports (following CTCAE V.5 criteria), physical examinations, and laboratory safety evaluations. These results will be tabulated overall and by dose level to examine their frequency, organ systems affected, severity, and relationship to study drugs.

The goal of the expansion cohort will be to further assess the tolerability of decitabine plus ipilimumab. Frequency of grade 3 or higher non-hematologic toxicities will be reported by arm and frequency of all grade immune-related adverse events will be reported by arm. Additionally, GVHD for the patients on the post-transplant arm will be estimated and reported with a 90% exact binomial confidence interval.

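### On its natural reading, 5.2 counts a grade 3 ipilimumab infusion reaction as a DLT only if it recurs, but a reaction handled as severe under 6.3.1 ends ipilimumab and so cannot recur

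*Combined protocol and SAP*

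**What the plan says.** Section 5.2 of the combined protocol and SAP makes non-hematologic toxicity of grade 3 or above a DLT by default, subject to exceptions. The infusion-reaction bullet first names grade 3 ipilimumab infusion reactions and then, after a semicolon, continues: "a second consecutive occurrence or grade 4 or high infusion reaction will be considered a DLT". DLTs are graded by CTCAE v5.0 over the 56 days from cycle 1 day 1.

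Section 6.3.1 manages infusion reactions by symptom tier, not by grade. After a moderate reaction the infusion may be resumed and the next scheduled dose may be given. For the severe tier (its examples include bronchospasm, angioedema and systolic pressure under 80 mm Hg) the infusion is stopped, the line is disconnected, and "No further ipilimumab will be administered". Section 6.2 separately requires permanent discontinuation for severe or life-threatening adverse reactions, after which "participants will have the option to continue decitabine alone on study" if judged to be benefitting.

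Section 13.1 governs evaluability: "Any patient who does not complete cycle 1 for any reason other than DLT will be considered non-evaluable for dose escalation decisions"; such patients are replaced. Sections 5.1 and 13.1 add that after 0 of 3 DLTs "the dose level may still be expanded to 6 evaluable patients based on observed toxicity at the current dose level", at the overall PI's discretion.

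**The concern.** The repeat test presumes a second infusion, and the severe-tier rule rules one out. The two rules together can therefore rank events in the wrong order: a grade 3 reaction mild enough to be re-dosed counts if it comes back, while one serious enough to end the drug does not count at all.

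DLT status drives every 3+3 decision, and hence the MTD or RP2D that is the primary objective in each arm. It also feeds the expansion-cohort trigger of 2 or more DLTs in 6 patients (5.3). With three patients at a level, one uncounted event can decide whether the dose is escalated.

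**Working it through.** **Following the patient through the rules**

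1. Two ipilimumab doses are scheduled in the 56-day window, nominally on days 1 and 29 (28-day cycles). A reaction at dose 1 that is re-dosed and recurs at dose 2 can meet the repeat test. A grade 4 or higher reaction counts at once.
2. After a severe-tier reaction the number of later infusions is zero, so a second consecutive reaction is impossible.
3. No other rule brings the event back into the count. The exceptions in 6.2.1 do not mention infusion reactions. Under 5.2, removal after a dosing delay of more than 4 weeks is a DLT only if the causal event already is one. The 5.2 allowance for judging events dose-limiting case by case concerns events after week 8.
4. If the patient completes cycle 1 (for example on decitabine alone), or reacts at dose 2 with cycle 1 already complete, the patient is evaluable with no DLT. Section 13.1 sets no minimum ipilimumab exposure. If cycle 1 is not completed, the patient is replaced.

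**The plan's own table (13.1)**

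P(escalate) = (1−p)³ + 3p(1−p)²(1−p)³. At p = 0.10, 0.20, 0.30, 0.40, 0.50 this gives 0.906, 0.709, 0.494, 0.309, 0.172. The plan states 0.91, 0.71, 0.49, 0.31, 0.17, so the table reproduces.

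**Conditional illustration**

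Suppose one of the first three patients has a grade 3 reaction that ends ipilimumab and has no other DLT. Let d be the DLT rate from other causes and q = 1−d. Assume independent patients and no further such reaction in the cohort.

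| Handling of the patient | P(escalate) | d = 0.10 | d = 0.20 | d = 0.30 |
|---|---|---|---|---|
| Evaluable, event not counted | q² + 2dq·q³ | 0.941 | 0.804 | 0.634 |
| Not counted; PI expands 0/3 to 6; at most 1/6 then required | q⁵ + 5dq⁴ | 0.919 | 0.737 | 0.528 |
| Replaced by a fresh patient | q³ + 3dq⁵ | 0.906 | 0.709 | 0.494 |
| Event counted as a DLT | q⁵ | 0.590 | 0.328 | 0.168 |

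The requirement of at most 1 in 6 after discretionary expansion is assumed from the plan's 1/6 rule.

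**Unconditional illustration**

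The documents give no rate for these reactions. The ipilimumab risk list in 7.1.1 puts infusion related reaction in its 20%-or-less column, with no split by grade. Let r be an assumed per-patient rate, added to d, and compare the table formula at p = d (not counted) with p = d + r (counted).

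| d | Not counted | r = 0.01 | r = 0.03 | r = 0.05 |
|---|---|---|---|---|
| 0.20 | 0.709 | 0.687 (−0.022) | 0.643 (−0.065) | 0.600 (−0.109) |
| 0.30 | 0.494 | 0.474 (−0.020) | 0.434 (−0.060) | 0.396 (−0.098) |

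**The case against.** **The bullet may already count a first reaction.** It stands in the list of DLTs, it opens by naming grade 3 infusion reactions, and it does not say that only a repeat counts. Infusion reactions are also absent from the sub-list of exceptions to the grade 3 rule. On that reading the gap disappears. It is the less natural reading, because the recurrence clause would be redundant and the neighbouring bullets are exemptions, but the text does not exclude it. An ambiguous DLT rule is itself a reason to reword.

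**Ending the drug is not this plan's test for a DLT.** The delay rule in 5.2 shows as much. Grade 3 immune-related events "that respond to corticosteroids and improve to grade 1 or less within 4 weeks will NOT count as DLTs", yet section 6.2 permanently stops ipilimumab for such events when they need prednisone at 1 to 2 mg/kg/day. A reader might therefore infer that every drug-ending event ought to be a DLT, and the documents do not support that. The narrower point stands: the immune-related exemption has a recovery test that can be failed without re-dosing, and the infusion-reaction exemption does not.

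**The affected group may be small.** Some severe-tier reactions may be grade 4 and count at once. Some grade 3 reactions may be handled as moderate and re-dosed. This is correct, and the documents do not allow the remainder to be sized. Section 6.3 also introduces its guidance as suggested, but the severe-tier instruction is directive and 6.2 independently stops the drug.

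**The event would be seen.** Sites must notify the overall PI of ipilimumab-related events of grade 3 or above (7.3.3). The PI signs off every escalation decision and holds at least monthly calls with the CTEP Medical Officer (12.1). At least six patients are required at the recommended dose (5.2). These safeguards, with the option to expand 0/3 to 6, reduce the risk of an unexamined escalation. None of them makes the event a DLT.

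**Conclusion.** The concern holds for a subset: first grade 3 infusion reactions that are managed as severe under 6.3.1, on the more natural reading of the 5.2 bullet. For these patients the recurrence test cannot be met, and the event drops out of the 3+3 count.

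Two stronger conclusions might be inferred and should not be. The first is that no grade 3 infusion reaction can ever be a DLT; a reaction at dose 1 that is re-dosed and recurs at dose 2 is one. The second is that the trial's escalation probability is inflated by the distance between 0.94 and 0.59. Those figures apply only once such a reaction has occurred among the first three patients, with a 10% DLT rate from other causes. If the patient is replaced, the figures equal the plan's own table. The overall shift, at other-cause rates of 20 to 30%, is about 2 points if such reactions occur in 1% of patients and 10 to 11 points at 5%. Both reaction rates are assumptions, not document figures.

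Severity is minor to moderate: the frequency is unknown and oversight is real, but the rule feeds the primary endpoint and is easily repaired.

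**What to change.** Replace the 5.2 bullet with:

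> A first grade 3 ipilimumab infusion reaction is not a DLT if ipilimumab is re-dosed and the reaction does not recur at the next consecutive dose. A grade 3 reaction that permanently stops ipilimumab under 6.3.1 within the 56-day window, a second consecutive grade 3 reaction, or any grade 4 or higher reaction is a DLT.

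Leave the 6.3.1 stopping rule unchanged. Because the event becomes a DLT, 13.1 no longer allows the patient to be replaced. The wording keeps the exemption for patients who are re-dosed and otherwise restores the plan's own default for grade 3 non-hematologic toxicity. If the sponsor did intend to exempt a first drug-ending reaction, 5.2 should say so and state whether the patient is evaluable or replaced.

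The cost is one or two sentences in an amendment, with no added visits or data. The downside is that a dose level may occasionally be expanded or stopped for a manageable reaction that may not be dose-related.

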3.2 Exclusion Criteria

3.2.1 Participants who have had chemotherapy or radiotherapy within 2 weeks prior to treatment start or those who have not recovered from adverse events due to agents administered more than 2 weeks prior to treatment start.

- Hydroxyurea is allowed for symptomatic leukocytosis if clinically necessary. A total white blood cell (WBC) count $< 25 \times 10^9/L$ prior to first dose of decitabine on trial is required. Prior leukapheresis and/or prior or concurrent treatment with hydroxyurea to achieve this level are allowed.
- Ongoing concurrent hormonal therapy is allowed

3.2.2 Participants with known CNS involvement with leukemia or who are receiving intrathecal chemotherapy for active CNS leukemia

- Those with a history of CNS involvement that has been completely treated and those who require intrathecal chemotherapy prophylaxis are eligible in the expansion cohorts

3.2.3 Prior HMA therapy is allowed, however this study *excludes* patients with progression or relapse that occur while receiving HMA-based therapy within 12 weeks prior to treatment start on study.

Disease progression is defined as either: (1) patients with prior MDS who progress to AML (defined by the presence of $\geq 20\%$ blasts in peripheral blood or bone marrow) on HMA-based therapy; OR (2) patients with AML with evidence of progressive disease according to ELN 2017 criteria (Appendix H for details) (e.g.

>50% increase in marrow blasts over baseline or >50% increase in peripheral blasts to > 25 x10⁹/L (>25,000/uL) (in absence of differentiation syndrome)).

(Note: Patients who relapse post-transplant who received HMA treatment prior to transplant are eligible for study.)

- 3.2.4 Donor lymphocyte infusion within 8 weeks prior to treatment start if post-transplant.
- 3.2.5 For patients that are post-transplant, ineligible patients include those with a history of overall grade III or IV (severe) acute GVHD at any time even if resolved.
- 3.2.6 Patients with a history of prior treatment with anti-CTLA-4 antibody, anti-PD 1 antibody, or anti- PDL1 antibody.
- 3.2.7 Participants who are receiving any other investigational agents.
- 3.2.8 Participants with known CNS involvement with leukemia or who are receiving intrathecal chemotherapy that is either prophylactic or therapeutic. History of CNS involvement that has been completely treated (no longer receiving intrathecal chemotherapy) will be allowed.

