- There will be three phases: priming, induction and maintenance
- Hydroxyurea may be used to control leukocytosis
- **Lead In: Priming phase with decitabine alone**
 - **Treatment:** Decitabine 20 mg/m² IV daily over 60 minutes (+/- 15 minutes) x 5 consecutive doses on **days 1-5** given per institutional guidelines
 - **Pre-medication prior to chemotherapy:** per institutional standards
 - Supportive medication such as allopurinol or equivalent should be considered in patients with white blood cell counts $> 10 \times 10^9 / L$ to reduce risk of tumor lysis syndrome.
 - Clinic visits on day 1 and day 15 (+/- 3 days)
 - Labs on day 1 and day 15 (+/- 3 days)
 - Research blood and aspirate collection at the end of the lead in period on a day between days 24-28 (see correlative calendar in [section 10.2](#)).
 - Adverse event evaluation:
 - **Intolerability during priming phase:** If a patient experiences unexpected intolerance to decitabine during the lead in that cannot be ameliorated by supportive care measures, then that patient will not continue on trial and will be replaced.
 - **Graft versus host disease (GVHD):** If there is evidence of acute GVHD that requires the use of systemic corticosteroids agents during the lead in, then the patient will be taken off study due to concern for safety with checkpoint blockade and replaced.
- **Cycles 1-4: Induction phase with combination decitabine and ipilimumab**
 - **Pre-Treatment Requirements**
 - Hematologic criteria to start cycle 1: None required
 - Hematologic criteria to start cycle 2:
 - If there is persistent disease (e.g. peripheral blasts, any marrow disease, persistent leukemia cutis or other form of extramedullary disease) at the time of disease response evaluation at the end of cycle 1, then there are no hematologic requirements to start cycle.
 - In the absence of disease, patients must have an absolute neutrophil count $\geq 500 \times 10^9 / L$ or platelet count to $\geq 25,000 \times 10^9 / L$ to proceed; otherwise administration of treatment will be delayed.
 - Hematologic criteria to start cycle 3:
 - If there is persistent disease (e.g. peripheral blasts, any marrow disease, persistent leukemia cutis or other form of extramedullary disease) at the time of disease response evaluation at the end of cycle 2, then there are no hematologic requirements to start cycle.

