 - In the absence of disease, patients must have an absolute neutrophil count $\geq 500 \times 10^9 / L$ or platelet count to $\geq 25,000 \times 10^9 / L$ to proceed.
 - Hematologic criteria to start cycle 4:
 - If there is persistent disease (e.g. peripheral blasts, any marrow disease, persistent leukemia cutis or other form of extramedullary

disease), then there are no hematologic requirements to start cycle .

- In the absence of disease, patients must have an absolute neutrophil count $\geq 500 \times 10^9/L$ or platelet count to $\geq 25,000 \times 10^9/L$ to proceed; otherwise administration of treatment will be delayed.

- **Treatment**

- Decitabine 20 mg/m² IV daily over 60 minutes (+/- 15 minutes) x 5 consecutive doses on **days 1-5** every 4 weeks given per institutional guidelines
 - **Pre-medication prior to chemotherapy:** per institutional standards
- Ipilimumab IV (per dose level as in table above) on **day 1** over 90 minutes (+/- 15 minutes) every 4 weeks for a total of 4 doses during induction
 - Dose escalation levels: 3 mg/kg (**starting dose**, dose level 0), 5 mg/kg (dose level 1), and 10 mg/kg (dose level 2)
 - Dose de-escalation level: 1 mg/kg
- Decitabine will be dosed prior to ipilimumab on day 1
- Vitals signs will be repeated hourly from time of ipilimumab infusion for up to two hours after infusion ends (+/- 30 minutes) on day 1 after first dose and up to one hour after infusion ends (+/- 30 minutes) on day 1 for subsequent doses.

- Clinic visits (including physical exam, medication review, ECOG and AE review)
 - Cycle 1: on day 1 and day 15 (+/- 3 days)
 - Cycles 2-4: on day 1 (+/- 3 days).

- **Procedures:**

- Labs
 - Cycle 1: on day 1, day 15 (+/- 3 days).
 - Cycles 2-4: on day 1 (+/- 3 days).
 - End of cycles 1, 2 and 4 on day of bone marrow biopsy (on a day between days 24-28).
- Bone marrow biopsy (including aspirate (if aspirable), core, flow cytometry, cytogenetics) will be at the end of cycles 1, 2 and 4 (on a day between days 24-28) for response assessment.
- If sole extramedullary disease (unless leukemia cutis), routine evaluation may include PET imaging (if FDG avid at time of diagnosis) at the end of cycles 2 and 4 (on a day between days 24-28) for response assessment.

- **Correlative studies:** peripheral blood and aspirate collection at the end of cycles 1, 2 and 4 on a day between days 24-28 (see correlative calendar in [section 10.2](#)).

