- The DLT window will be the first 8 weeks of combination treatment with decitabine and ipilimumab (starting day 1 of cycle 1).
- At the time of response assessments, patients with evidence of disease progression will come off study unless they have evidence of treatment tolerability and clinical benefit (i.e. improvement in transfusion frequency or peripheral blast reduction or symptom improvement). Patients with evidence of disease progression may be allowed to stay on study if deriving clinical benefit with approval from the overall PI as there may be a delayed response with

- immunotherapy.
- Patients with stable disease or better at the end of cycle 4 will move forward with treatment in the maintenance phase.
- **Cycles 5-12: Maintenance phase with combination decitabine and ipilimumab**
 - Pre-treatment Criteria
 - In the absence of disease, patients should have an absolute neutrophil count $\geq 500 \times 10^9/L$ or platelet count to $\geq 25,000 \times 10^9/L$ to proceed with each cycle. Dose delay recommendations are provided in section 6.
 - If there is still disease (partial or stable) then no hematologic requirements are required to start cycle
 - Treatment
 - Decitabine 20 mg/m² IV daily over 60 minutes (+/- 15 minutes) x 5 consecutive doses on **days 1-5** every 4 weeks given per institutional guidelines
 - **Pre-medication prior to chemotherapy:** per institutional standards
 - Ipilimumab IV (per dose level as in table above) on **day 1** over 90 minutes (+/- 15 minutes) every **8 weeks** for a total of 4 doses during maintenance
 - Decitabine will be dosed prior to ipilimumab on day 1
 - Vitals signs will be repeated hourly from time of ipilimumab infusion for up to one hour after infusion ends (+/- 30 minutes) on day 1.
 - Clinic visits (including physical exam, medication review, ECOG and AE review)
 - Cycles 5-12: on day 1 (+/- 3 days).
 - Procedures:
 - Labs
 - Cycles 5-12: on day 1 (+/- 3 days).
 - At the end of cycles 7 and 10 on a day between days 24-28 and at end of study on a day between days 24-28.
 - Bone marrow biopsy (including aspirate (if aspirable), core, flow cytometry, cytogenetics) will be at the end of cycles 7, 10 and at end of study (on a day between days 24-28) for response assessment.
 - Correlative studies: peripheral blood and aspirate collection at the end of cycles 7 and 10 on a day between days 24-28 and at the end of study (see correlative calendar in [section 10.2](#)).

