7.3.4 Additional Protocol-Specific Expedited Adverse Event Reporting Exclusions

For this protocol only, the AEs/grades listed below do not require expedited reporting via CTEP-AERS. However, they still must be reported through the routine reporting mechanism ([Section 7.4](#)). All events except those specifically mentioned the SPEER and listed below must be reported via CTEP AERS:

- Grade 2 or 3 (<3000/mm³-1000/mm³) White Blood Cell Count Decrease
- Grade 2 or 3 (<1500/mm³-500/mm³) Absolute Neutrophil Count Decrease
- Grade 2 or 3 (<75,000/mm³-25,000/mm³) Platelet Count Decrease

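### The neutrophil and platelet thresholds in the DLT definition (5.2) and the cycle-start criteria (5.1) are printed 1000 times too high

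*Combined protocol and SAP*

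**What the plan says.** **DLT definition (5.2).** Hematologic toxicity of grade 4 or higher is dose-limiting if, with a hypocellular marrow and no underlying disease, the patient does not recover "absolute neutrophil count to $\geq 500 \times 10^9/L$ or platelet count to $\geq 25,000 \times 10^9/L$, at the end of the DLT window". As for every DLT, the event must be at least possibly related to the combination and "not related to underlying disease or intercurrent illness or to decitabine alone".

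**Cycle-start criteria (5.1).** For those without disease, the rule at cycle 2 is that "patients must have an absolute neutrophil count $\geq 500 \times 10^9 / L$ or platelet count to $\geq 25,000 \times 10^9 / L$ to proceed". Cycles 3 and 4 carry the same figures and unit. For maintenance, disease-free "patients should have an absolute neutrophil count $\geq 500 \times 10^9/L$ or platelet count to $\geq 25,000 \times 10^9/L$ to proceed with each cycle". Patients with persistent disease have no hematologic requirement.

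**The same boundaries elsewhere.** Section 7.3.4 lists as exempt from expedited reporting "Grade 2 or 3 (<1500/mm³-500/mm³) Absolute Neutrophil Count Decrease" and "Grade 2 or 3 (<75,000/mm³-25,000/mm³) Platelet Count Decrease". The lower ends of those ranges are where grade 3 stops and grade 4 begins. In 3.2.3 the protocol converts units correctly, writing "> 25 x10⁹/L (>25,000/uL" for peripheral blasts. Appendix H likewise equates an ANC of 0.5 × 10⁹/L with 500 per microlitre.

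**The concern.** The figures 500 and 25,000 are the familiar grade 3/4 cut-points when expressed per mm³. In 5.1 and 5.2 they carry the unit × 10⁹/L, in which no patient could reach them.

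This matters because the 5.2 clause is part of the DLT definition, and DLT counts alone decide the MTD/RP2D, the primary objective for both arms. On the literal wording, recovered and unrecovered patients are treated alike: any grade 4 cytopenia that passes the attribution filter, with a hypocellular disease-free marrow, is a DLT. In 5.1 a disease-free patient could never satisfy the mandatory criterion for cycles 2 to 4. Section 6.2 normally takes patients off treatment when ipilimumab is delayed by more than 4 weeks, so literal compliance would penalise the patients who had cleared their disease.

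A second, smaller problem sits in the same 5.2 sentence. Failing to recover one count *or* the other can mean that neither lineage recovered, or that at least one did not. Correcting the unit does not settle which is meant.

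**Working it through.** **Inputs**

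- Printed threshold (5.2, and 5.1 for cycles 2, 3, 4 and maintenance): ANC 500 × 10⁹/L, platelets 25,000 × 10⁹/L.
- Lower end of grade 3 (7.3.4): ANC 500/mm³, platelets 25,000/mm³.
- Morphological CR (Appendix D): ANC >1.0 × 10⁹/L, platelets >100 × 10⁹/L.
- Total WBC allowed before the first decitabine dose (3.2.1): <25 × 10⁹/L.

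**Conversion.** 1 mm³ = 1 µL and 10⁶ µL = 1 L, so 1/mm³ = 10⁶/L = 0.001 × 10⁹/L.

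| | 7.3.4 boundary | In × 10⁹/L | Printed in 5.1/5.2 | Ratio | Printed value per mm³ |
|---|---|---|---|---|---|
| ANC | 500/mm³ | 500 × 0.001 = 0.5 | 500 × 10⁹/L | 500/0.5 = 1000 | 500,000 |
| Platelets | 25,000/mm³ | 25,000 × 0.001 = 25 | 25,000 × 10⁹/L | 25,000/25 = 1000 | 25,000,000 |

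The printed thresholds therefore do not reproduce in the stated unit. With the unit corrected they match 7.3.4 exactly.

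**Plausibility.** The printed values are 500/1.0 = 500 times the CR threshold for ANC and 25,000/100 = 250 times that for platelets. The printed ANC is also 500/25 = 20 times the maximum total WBC at first dosing, although neutrophils are a subset of white cells.

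**Extent.** One DLT clause plus four start criteria (cycles 2, 3, 4, maintenance) gives 5 places × 2 figures = 10 figures. The repetition, with correct × 10⁹/L values elsewhere in the protocol (the WBC level for allopurinol in 5.1 itself, 3.2.1, 3.2.3, Appendices D and H), makes a text-extraction fault unlikely.

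**Effect of one misclassified patient under the 5.2 escalation table**

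- 0/3 becomes 1/3: at least 3 more patients at that dose instead of escalation.
- 1/6 becomes 2/6: escalation stops.

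**What does not depend on the threshold.** The escalation probabilities in 13.1 follow from P(escalate) = q³ + 3pq⁵, where p is the true DLT rate and q = 1 − p. For p = 0.10, 0.20, 0.30, 0.40, 0.50 this gives 0.906, 0.709, 0.494, 0.309, 0.172, which agrees with the printed 0.91, 0.71, 0.49, 0.31, 0.17. The table and the sample size stand.

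**The *or*, with units corrected.** Take a patient at day 56 with ANC 0.3 and platelets 40 × 10⁹/L who otherwise meets the clause.

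- Under 5.1, one sufficient lineage is enough (40 ≥ 25), so the patient may proceed.
- Under 5.2, read as neither lineage recovered: not a DLT.
- Under 5.2, read as either lineage failed (0.3 < 0.5): a DLT.

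**The case against.** The best defence is that the slip announces itself. No one can have an ANC of 500 × 10⁹/L, the clause begins from grade 4 toxicity, and recovery out of grade 4 is the obvious intent, so a clinician would read the numbers per mm³. Even taken literally, the clause needs attribution to the combination, a hypocellular marrow and no disease. Escalation decisions need sign-off by the Protocol Principal Investigator, with calls at least monthly that include the CTEP Medical Officer (12.1). Sections 6 and 6.1 give discretion over decitabine delays and assume that disease-free patients ordinarily continue. Maintenance says only that patients should meet the counts. Section 7.3.4 is a list of reporting exclusions and does not itself name a grade 3/4 boundary. Finally, the natural English reading of the *or* is that neither lineage recovered, which is the complement of 5.1.

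Most of this stands as a limit on likely harm. It does not make the text right. A threshold that classifies the primary endpoint should not rely on each site silently correcting it, and discretion in Section 6 does not repair a mandatory criterion in 5.1. The boundary is an inference from 7.3.4, but a secure one, since the protocol's own conversions in 3.2.3 and Appendix H support it. On the *or*, the neither-recovered reading is probably intended. The wording still admits the other, so this is a clarification and the conclusion does not rest on it.

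**Conclusion.** The concern holds. The ANC and platelet thresholds in the hematologic DLT clause and in four cycle-start criteria are wrong as written, each by a factor of exactly 1000. The conclusion rests only on the unit conversion and on taking the lower ends of the 7.3.4 grade 3 ranges as the intended values.

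The consequence for dose escalation is conditional. If the text were applied literally to a single patient, it could add a cohort or stop escalation. How often the clause would apply cannot be estimated from the documents, and most readers would probably infer the right values. It should be corrected because it sits in the definition that determines the MTD/RP2D.

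**What to change.** In 5.2 (one place) and 5.1 (cycles 2, 3, 4 and maintenance), replace the figures with ANC ≥0.5 × 10⁹/L (500/mm³) and platelets ≥25 × 10⁹/L (25,000/mm³).

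In 5.2, also say whether a DLT requires failure of both lineages or of either. If the complement of 5.1 is meant, suitable wording is: *neither ANC ≥0.5 × 10⁹/L nor platelets ≥25 × 10⁹/L has been reached by the end of the DLT window*. If failure of either lineage is meant, say so, and note that a patient can then be allowed to start a cycle under 5.1 and still count as a DLT.

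The cost is a wording amendment in five places. The design, the 13.1 escalation table and the sample size are unchanged.
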